For the OS interim and final analyses, all the events reported in the database at time of database lock will be used for the primary analyses.

Primary Efficacy Measures

Overall survival (OS). OS is defined as the time between the date of randomization and the date of death. For subjects without documentation of death, OS will be censored on the last date the subject was known to be alive.

Progression-free Survival (PFS) as assessed by BICR is defined as the time from randomization to the date of the first documented PD per BICR or death due to any cause. Subjects who die without a reported prior PD per BICR (and die without start of subsequent therapy) will be considered to have progressed on the date of death. Subjects who did not have documented PD per BICR per RECIST1.1 criteria and who did not die, will be censored at the date of the last evaluable tumor assessment on or prior to initiation of subsequent anti-cancer therapy. Subjects who did not have any on-study tumor assessments and did not die (or died after initiation of subsequent anti-cancer therapy) will be censored

Revised Protocol No.: 09

Date: 16-Sep-2019

b Results based on simulations

^c Number of events for the nivolumab plus chemotherapy vs. chemotherapy comparison in total.

d After first patient randomized to nivolumab + chemotherapy or chemotherapy in 1:1:1 randomization.

e Significance levels will be calculated based on the actual number of deaths at each interim analysis

at the randomization date. Subjects who started any subsequent anti-cancer therapy without a prior reported PD per BICR will be censored at the last tumor assessment prior to or on the initiation of the subsequent anti-cancer therapy.

Secondary Efficacy Measures

Time to Symptom Deterioration (TTSD) is defined as the time from randomization until a clinically meaningful decline from baseline in GaCS score. A clinically meaningful deterioration is defined as a reduction of 8.2 points in the GaCS score. Subjects who do not deteriorate will be censored at the time of their last GACS assessment. Subjects without baseline GaCS assessment will be censored on the randomization date. Those with baseline GaCS, who do not have any GaCS assessments after randomization will be censored on the day after randomization.

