8.4.2.3 Analyses for Secondary Objectives in Hierarchy

Nivolumab plus Chemotherapy vs Chemotherapy

OS in CPS \geq 1 and all randomized will be compared using a two-sided log rank test stratified by the same stratification factors as the primary endpoint. The HR with its associated two-sided CI will be estimated via a stratified Cox model with treatment arm as the only covariate in the model. OS for each treatment arm will be estimated and plotted using the Kaplan-Meier (KM) product-limit method. Median survival time along with 95% CI will be constructed based on a log-log transformed CI for the survival function.

Nivolumab plus Ipilimumab vs Chemotherapy

Overall survival in subjects with PD-L1 by CPS \geq 5 and all randomized will be compared between nivolumab plus ipilimumab vs chemotherapy using a two-sided log rank test stratified by region (Asia vs US vs rest of world), ECOG status (0 vs 1) and TPS PD-L1 (\geq 1% vs < 1% or indeterminate) and as recorded in the IRT.

The HR with its associated two-sided CI will be estimated via a stratified Cox model with treatment arm as the only covariate in the model. OS for each treatment arm will be estimated and plotted using the Kaplan-Meier (KM) product-limit method. Median survival time along with 95% CI will be constructed based on a log-log transformed CI for the survival function.

Same methods will be used to analyze OS in subjects with PD-L1 by CPS \geq 10 and 1.

Similar methodology will be used for TTSD.

Exploratory Endpoints

Progression-free Survival (PFS) as assessed by BICR/ investigator will be estimated and plotted using the KM product limit method for each treatment arm. Median survival time along with 95% CI will be constructed based on a log-log transformed CI for the survival function. The HR with its associated two-sided 95% CI will be estimated via a stratified Cox model with treatment arm as the only covariate in the model.

Best Overall Response will be summarized by response category for each treatment group.

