### **4.2.2.4 Time to Symptom Deterioration**

Time to symptom deterioration is defined as the time from randomization until a clinically meaningful decline from baseline in GaCS score. A clinically meaningful deterioration is defined as a reduction of 8.2 points in the GaCS score. Only events before treatment discontinuation will be taken into account: patients who do not deteriorate before treatment discontinuation will be censored at the time of their last on-treatment GaCS assessment. Those who have no GaCS assessments after randomization and those who were never treated will be censored on the date of randomization. For more details on the GaCS scale, see [Section 4.3.3](#). Secondary objectives are the comparison of TTSD between nivo+ipi and chemo in PD-L1 CPS  $\geq 5$  subjects and all randomized subjects.

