**Table 7.5-1: Stratification Factors Used for Stratified Analyses**

[figure not shown]
	Nivo+ipi vs. Chemotherapy	Nivo+chemo vs. Chemotherapy
	
 
• Region (Asia vs. US vs. RoW)
 
• ECOG performance status (0 vs. 1)
 
• PD-L1 expression level (<math>\geq 1\%</math> vs. <math>< 1\%</math> or indeterminate)
 
	
 
• Region (Asia vs. US vs. RoW)
 
• ECOG performance status (0 vs. 1)
 
• PD-L1 expression level (<math>\geq 1\%</math> vs. <math>< 1\%</math> or indeterminate)
 
• Chemotherapy (XELOX vs. FOLFOX)
 

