#### 7.9.1 FACT-Ga and TTSD

TTSD is an exploratory endpoint for the comparison of nivo+chemo vs. chemo and the analyses of TTSD will be descriptive. TTSD is a secondary objective for the comparison of nivo+ipi vs. chemo in the hierarchy and will be tested formally if the preceding secondary endpoint in the hierarchy is significant. See section 4.2.2.4 for the definition of TTSD.

TTSD will be assessed for the different CPS cutoffs and for all randomized subjects.

TTSD will be compared between nivo+ipi and chemo via stratified log-rank test at a two-sided  $\alpha$  level with  $\alpha$  inherited from the preceding endpoint in hierarchy. The two-sided log-rank p-value will be reported.

The estimate of the TTSD hazard ratio between treatment groups will be calculated using a stratified Cox proportional hazards model, with treatment as the sole indicator covariate (for each pair of treatment arms separately). Ties will be handled using the exact method. A two-sided 95% for the hazard ratio will also be presented. CI In case TTSD is formally tested the 100 x (1 -  $\alpha$ )% CI will be provided.

The TTSD function for each treatment group will be estimated using the KM product limit method and will be displayed graphically. Medians and two-sided 95% CI in each treatment group will be computed via the log-log transformation method.

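### Time to symptom deterioration is a fall from the subject's own baseline GaCS, but no planned TTSD analysis adjusts for that baseline score

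*Protocol*

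**What the plan says.** The Protocol (Synopsis, Secondary Efficacy Measures, and 8.3.2) sets the event: "A clinically meaningful deterioration is defined as a reduction of 8.2 points in the GaCS score". SAP 4.2.2.4 measures "the time from randomization until a clinically meaningful decline from baseline in GaCS score" and counts only events before treatment discontinuation.

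For N+I versus chemotherapy, SAP Table 4-1 marks TTSD as controlled for Type I error, and SAP 7.9.1 says it "will be tested formally if the preceding secondary endpoint in the hierarchy is significant". The method in 7.9.1 is: "TTSD will be compared between nivo+ipi and chemo via stratified log-rank test at a two-sided" level inherited from the preceding endpoint. The hazard ratio comes from a "stratified Cox proportional hazards model, with treatment as the sole indicator covariate (for each pair of treatment arms separately"). The strata in SAP Table 7.5-1 are region, ECOG status and tumor-cell PD-L1. Protocol 8.4.2.3, after describing the OS analysis, says "Similar methodology will be used for TTSD".

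The three TTSD sensitivity analyses in SAP 7.9.1 change the source of the strata, the handling of death, and the use of assessments on or after discontinuation. None uses baseline GaCS. The multivariable Cox models in SAP 7.5.2.2, 7.5.2.5 and 7.5.3.2 are for PFS and OS only, and their factor list does not include GaCS. Protocol Tables 5.1-2, 5.1-3 and 5.1-4 schedule FACT-Ga at Cycle 1 Day 1 in all three arms.

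**The concern.** The baseline score is part of the event rule, so it can predict the event. A baseline that reads high through measurement error brings the 8.2-point fall closer; taking change from baseline does not remove this. Randomization was not stratified by GaCS. If the arms differ on it by chance, the treatment-only hazard ratio moves with the difference, and no planned analysis shows by how much.

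For OS in the same comparison, SAP 7.5.3.2 plans a prognostic-factor model and a check for imbalance in the CPS ≥ 5 population. TTSD has neither. What is at stake is the precision of one hazard ratio and its protection from chance imbalance, using a variable already in the database.

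**Working it through.** **Inputs from the documents.** Fall of 8.2 points; 19 items scored 0-4, so 19 × 4 = 76 at most if the score is the item sum (assumed); visits every 6 weeks; 815 subjects in N+I versus chemotherapy (SAP 5.1), of whom 489 are expected to have CPS ≥ 5 (SAP Appendix 5) or 285 at the design prevalence; two-sided alpha 0.035 (SAP Appendix 5).

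**Not in the documents.** GaCS variance, TTSD hazard ratio, TTSD events and TTSD power. All are assumed below.

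**Step 1, the plan's own figures.** There is no TTSD figure to reproduce. As a check on the same comparison, OS power = Φ(½√d·|ln HR| − z) at HR 0.70 gives:
- 240 events, alpha 0.015: 2.763 − 2.432 = 0.330, power 63.0% (stated 63%).
- 240 events, alpha 0.035: 2.763 − 2.108 = 0.654, power 74.4% (stated 73%).
- 411 events, alpha 0.035: 3.615 − 2.108 = 1.507, power 93.4% (stated 93%).

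**Step 2, size of a chance imbalance.** In SD units the standard error of the baseline difference is √(4/N): 0.118 at N = 285, 0.090 at 489, 0.070 at 815. The 95% ranges (× 1.96) are about ±0.23, ±0.18 and ±0.14 SD.

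**Step 3, effect on the hazard ratio and power.** The simulation applies the 8.2-point rule to a 0-76 score: N = 489, true baseline mean 54 and SD 11, measurement SD 4 or 6, 6-weekly visits, random individual slopes, censoring at discontinuation, 1000 runs. The correlation is between the true baseline and the individual slope; a positive value means that sicker subjects decline faster. The shift is exp(0.1 × slope of the unadjusted log HR on imbalance) − 1.

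| Measurement SD | Correlation | Event HR per SD of baseline | Slope, unadjusted | Shift per 0.1 SD | Slope, adjusted | Power, unadjusted to adjusted |
|---|---|---|---|---|---|---|
| 4 | −0.3 | 1.57 | 0.322 | 3.3% | −0.11 | 79.9% to 80.6% |
| 4 | 0 | 1.18 | 0.229 | 2.3% | 0.05 | 76.0% to 77.5% |
| 4 | +0.3 | 0.92 | −0.049 | −0.5% | 0.04 | 75.4% to 75.7% |
| 6 | −0.3 | 1.66 | 0.468 | 4.8% | −0.01 | 59.1% to 63.3% |
| 6 | 0 | 1.37 | 0.306 | 3.1% | 0.00 | 59.3% to 60.9% |
| 6 | +0.3 | 1.14 | 0.115 | 1.2% | −0.02 | 57.5% to 57.5% |

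The slopes carry a simulation standard error of about 0.05: with 192 events, (2/√192)/(0.090 × √1000) = 0.051. The adjusted slopes are therefore compatible with zero, or nearly so.

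A second simulation (400 subjects, between-subject SD 9-11, measurement SD 4-6, true HR about 0.65) gave unadjusted slopes of 0.21-0.51. That is exp(0.021) − 1 = 2.1% to exp(0.051) − 1 = 5.2% per 0.1 SD, with adjusted slopes of −0.06 to 0.05. Power went from 56% to 56%, 68% to 71% and 68% to 72%.

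**Step 4, Type I error.** With no treatment effect, the rule-based simulation rejected in 2.6-4.2% of runs unadjusted and 3.1-4.2% adjusted, against 3.5% nominal (Monte Carlo standard error √(0.035 × 0.965/1000) = 0.6 points).

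The rule-based simulation left out the randomization strata and used the treatment-only Cox test in place of the log-rank.

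**The case against.** The case for leaving the plan alone is substantial.

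- **Randomization already handles this.** It balances baseline GaCS in expectation, the confidence interval reflects chance imbalance, and not stratifying on CPS ≥ 5 does not bias GaCS. This stands. A reader might infer that the TTSD test is invalid or its error rate inflated; Step 4 gives no support for that.
- **The gain is small.** ECOG is a stratum and plausibly tracks symptom burden, so the strata may recover part of it. This stands. A reader might infer a material loss of power. A plain proportional-hazards simulation does reach 72% to 85% at N = 489, but only by assuming an event HR of 2.0 per SD; the 8.2-point rule produced 0.92 to 1.66.
- **The floor.** A reader might infer that subjects with a baseline below 8.2, who can never have an event, drive the problem. With an assumed mean of 52 and total SD √(9² + 6²) = 10.8 to √(11² + 4²) = 11.7, a score of 8.2 lies 43.8/10.8 = 4.1 to 43.8/11.7 = 3.7 SD below the mean. That is fewer than 0.1 expected subjects in 815.
- **An imbalance would be visible.** SAP 7.9.1 tabulates mean GaCS by arm at each time point. True, but no adjusted estimate follows from it.
- **The formal test should not move.** A reader might infer that the p-value ought to come from the adjusted Cox model. The stratified log-rank is used across the hierarchy, and SAP v5.0 followed the nivolumab-plus-chemotherapy analysis. About 1098/3 = 366 of the 815/2 ≈ 407 chemotherapy subjects in this comparison were also in that one. Changing an error-controlled test at that stage is hard to defend.
- **Reach.** TTSD is tested only after the preceding N+I OS tests succeed, and TTSD for nivolumab plus chemotherapy is descriptive.

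One further limit: the Cycle 1 Day 1 score may be given after open-label randomization, so it is not strictly a pre-randomization covariate. The endpoint already depends on that score.

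**Conclusion.** The omission is real and the consequence modest. The formal test stands. The unadjusted TTSD hazard ratio moves with any chance baseline difference, by roughly 2-5% per 0.1 SD where the assumed association is moderate and by about 1% or less where sicker subjects decline faster. One standard error of imbalance is about 0.09 SD at N = 489 and 0.07 SD at N = 815. Adjustment removes most or all of the shift. The power gain is about 0-4 points and may be nil.

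The strength and even the sign of the baseline association are assumed, and the strata were left out of the rule-based simulation, so these are indicative sizes. This is a low-cost improvement in precision; it corrects no bias.

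**What to change.** In SAP 7.9.1, before the N+I versus chemotherapy database lock:

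- Add baseline GaCS as a continuous covariate to the stratified Cox model for TTSD. Report that hazard ratio and confidence interval, labelled as conditional on baseline, beside the treatment-only estimate.
- State explicitly that the stratified log-rank remains the formal hierarchical test.
- Use the same adjusted model for the descriptive nivolumab-plus-chemotherapy TTSD analysis.

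The cost is one model term and a few lines of text. No new data are needed and no events are lost: without a baseline score no decline can be shown, and such subjects are already censored at randomization (Protocol 8.3.2) or outside the FACT-Ga analysis set (SAP 7.9). The downside is that the adjusted hazard ratio is conditional on baseline and may differ slightly from the treatment-only estimate that accompanies the log-rank, so the report must say which figure goes with the formal p-value.

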1 INTRODUCTION AND STUDY RATIONALE

CA209649 is a Phase 3, randomized, open-label study of nivolumab plus ipilimumab or nivolumab in combination with oxaliplatin plus fluoropyrimidine vs oxaliplatin plus fluoropyrimidine in subjects with previously untreated advanced or metastatic gastroesophageal junction (GEJ) or gastric cancer (GC). This study will determine if nivolumab plus ipilimumab improves overall survival (OS) vs the standard of care, oxaliplatin plus fluoropyrimidine, in subjects with GC/GEJ cancer with enriched PD-L1 expression by combined positive score (CPS); or whether nivolumab in combination with oxaliplatin plus fluoropyrimidine improves OS or PFS vs the standard of care, oxaliplatin plus fluoropyrimidine, in subjects with GC/GEJ cancer with enriched PD-LI expressing by CPS. Additional objectives include further characterization of efficacy, safety and tolerability, pharmacokinetics (PK), patient-reported outcomes, and potential predictive biomarkers of nivolumab in combination with ipilimumab or nivolumab in combination with oxaliplatin plus fluoropyrimidine in subjects with GC/GEJ whose tumors do or do not express PD-L1.

1.1 Study Rationale

1.1.1 Rationale for Investigating Advanced or Metastatic GC/GEJ in the First Line Setting

Gastric cancer is the 5th leading cancer and the 3rd leading cause of cancer-related deaths worldwide. The incidence of GC varies with different geographic regions, with over 70% of GCs occurring in developing countries. ¹ Gastric cancer often presents as advanced disease upon diagnosis, comprising approximately 40% of newly diagnosed cases in the United States (US) and Europe, and approximately 20% in Japan and Korea, where early detection is common.²

Gastric cancer, including GEJ carcinoma, is a heterogeneous disease with several established risk factors, including environmental, genetic and behavioral risks. There has been a steady decline in GC mortality attributable to dietary and lifestyle changes worldwide³ and to decreasing infection with *Helicobacter pylori*, which is considered the main cause in Asian countries.⁴ However, the incidence of GEJ tumors and esophageal adenocarcinoma (EAC) has increased considerably due to increases in risk factors such as obesity and gastroesophageal reflux disease.¹

Gastroesophageal junction cancer anatomically straddles the distal esophagus and proximal stomach; due to its location and given that, like GC, the majority of GEJ tumors are adenocarcinomas, GEJ tumors are frequently grouped together with GC. Adenocarcinoma is further classified into 2 distinct types: intestinal (well-differentiated) or diffuse (undifferentiated).⁵

Until optimal, tumor-specific treatment strategies are defined, advanced and metastatic GEJ cancer is treated and managed in a similar fashion to GC.^{6,7} As current understanding of EAC's, are that they share similar disease and molecular characteristics⁸ as GEJ and GC adenocarcinomas, EACs are managed and treated similar to those tumors per treatment guidelines and clinical practice.^{9,10} Platinum compounds (oxaliplatin and cisplatin) and fluoropyrimidines (5-fluorouracil, capecitabine, and tegafur/gimeracil/oteracil potassium [S1]) are generally considered as first-line (1L), standard-of-care treatment options in metastatic GC and GEJ cancer across geographic

regions. ^{11,12,13} These platinum/fluoropyrimidine combinations are also generally accepted as active comparators in Phase 2 or Phase 3 randomized studies by health authorities worldwide. The different biological characteristics and treatment approaches among regions result in different survival outcomes, with median overall survival (mOS) durations of 12 to 14 months in Asian countries and 8 to 11 months in the US and Europe. ^{14,15,16}. While these cytotoxic agents are clinically active, with a 30% to 50% objective response rate (ORR) in the 1L GC treatment setting, this clinical activity is accompanied by high toxicity. ^{14,15,16,17} Grade 3/4 toxicities up to 77% have been reported for platinum doublets and > 80% for triplet regimens. ^{14,15,17,18} Hematological toxicity is the major problem; Grade 3/4 neutropenia has been reported in approximately 40% of patients treated with platinum doublets, and has increased to 82% when docetaxel was added on. ^{14,17,18} Renal toxicity and neuropathy are the main reasons for discontinuation of platinum treatment. Gastrointestinal complaints are also common. ^{14,15,17,18} In addition, despite ORRs of 30% to 50%, chemotherapy has resulted in few patients achieving complete response (CR); therefore, new treatment options are needed to improve survival and response as well as decrease toxicity in 1L GC/GEJ cancer.

In the past decade, multiple new investigational drugs with mainly molecular targets have been investigated in the 1L setting as add-ons to backbone platinum and fluoropyrimidine treatment. These agents, with the exception of trastuzumab, which targets the Her2-positive population, ¹⁹ have failed to show a survival benefit in randomized trials. The reasons include regional differences in efficacy, with the highest survival rate but smallest benefit noted in Asia and the shortest mOS but greatest benefit in Western countries. ^{14,18,19} Thus, a regional approach might be appropriate in 1L GC/GEJ treatment development, and this study will mainly focus on Western countries where great unmet medical needs are present.

1.1.2 Rationale for the Combined Targeting of PD-1 and CTLA-4 in Advanced or Metastatic GC/GEJ Cancer

Immunotherapeutic approaches have demonstrated clinical efficacy in several advanced cancer types, including melanoma, non-small cell lung cancer (NSCLC), renal cell carcinoma (RCC) and gastric cancer (GC). Nivolumab (BMS-936558), a programmed cell death protein-1 (PD-1) antibody, and ipilimumab (BMS-734016), a cytotoxic T-cell lymphoma-4 (CTLA-4) antibody, are such immunotherapies that have been approved in the US, Europe, Japan and other countries. 24,25,26,27

Preclinical data indicate that the combination of PD-1 and CTLA-4 receptor blockade may improve antitumor activity. ²⁸ In vitro combinations of nivolumab plus ipilimumab have increased IFN-γ production 2- to 7-fold over either agent alone in a mixed lymphocyte reaction. In a murine melanoma vaccine model, blockade with either CTLA-4 or PD-1 antibodies increased the proportion of CTLA-4- and PD-1-expressing CD4/CD8 tumor-infiltrating T-effector cells, and dual blockade increased tumor infiltration of T-effector cells and decreased intratumoral T regulatory cells, as compared to either agent alone. ²⁸ In the Phase 1 dose escalation study CA209004, the combination of nivolumab and ipilimumab has been studied in subjects with

unresectable or metastatic melanoma. In this study, a safe dose level for the combination of ipilimumab and nivolumab was established for the treatment of advanced melanoma. At this dose level, 3 mg/kg ipilimumab plus 1 mg/kg nivolumab, an objective response rate of 53% was observed. This dose level has been approved in subjects with advanced melanoma in the US based on the Phase 3 study CA209067. In this study, the combination of nivolumab and ipilimumab has demonstrated increased benefit compared to either ipilimumab or nivolumab monotherapies in subjects with advanced melanoma.²⁹

In GC patients, tumors with PD-L1 expression have been reported to be associated with depth of muscle invasion, tumor size, and lymph node metastasis. The survival of patients with PD-L1 or PD-L2 expressing tumors is significantly worse than for those patients without PD-L1/PD-L2 expressing tumors. PD-L1 or PD-L2 expressing tumors have been reported in approximately 22% to 40% of GC and PD-L1 has been suggested as a prognostic marker. More and more data of PD-L1 expression in GC has become available since this study was originally designed. These data suggest that PD-L1 is an independent prognosis factor while other data suggest that its use as prognosis factor may not be proven. 32,33,34,35,36

The blockage of PD-1/PD-L1/PD-L2 might improve the survival of GC patients. Anti PD-1 and PD-L1 inhibitors (eg, nivolumab, pembrolizumab, and avelumab) have been investigated in GC treatment and have demonstrated anti-tumor activity. 37,38 39

Treatment with pembrolizumab achieved a 33% ORR by investigator assessment and 22% by central data review in GC subjects with PD-L1 expressing tumors. ³⁸ The 6-month progression-free survival (PFS) rate was 26% and median PFS was 1.9 months (95% CI: 1.8, 3.5). The 6-month OS rate was 66% and mOS was 11.4 months (95% CI: 5.7, NR). PD-L1 expressing tumors (cutoff 1%) were reported in 40% of GC patients in this study, which is consistent with previous reports. ³⁸

Preliminary data for second line (2L) and switching maintenance use of avelumab, an anti-PD-L1 IgG1 antibody, in advanced GC have been recently reported. The ORRs were 15% and 7.3%, the 6-month PFS rates were 19% and 34%, and the median PFS were 2.9 months and 3.5 months in avelumab as 2L and switching maintenance therapy, respectively.³⁹

